7.1.3. Progression Free Survival (PFS) for Part 2 GBM cohort

Progression-free survival (PFS) is defined as the time (in months, interval in months is calculated by duration in days/30.4375) from date of first dose date of study drug until date of documented disease progression or death due to any cause, whichever comes first.

The PFS rate at 6 months for Part 2 GBM cohort will be estimated by the Kaplan-Meier method. These rates, estimate the proportion of patients who did not progress and were alive at month 6. The 95% confidence intervals for the PFS rate at month 6 will be estimated using Greenwood's estimate of the standard error (SE) and a log-log transformation of the progression-free survival function (Greenwood, 1926).

A summary of the assignments for progression and censoring dates for PFS is specified in the following table:

Table 10	Assignments	for Progression	and Censoring Dates	for PFS Analysis
	0	0	0	

1.	Situation	1.	Date of Event (Progression/ Death) or Censoring	1.	Outcome Event (Progression/ Death) or Censored
1.	No (or inadequate) baseline tumor assessments and the subject has not died (if the subject has died follow the rules for death indicted at the bottom of the table)	2.	Start Date of Treatment	2.	Censored
1.	No post-baseline assessments and the subject has not died (if the subject has died follow the rules for death indicted at the bottom of the table)	3.	Start Date of Treatment	3.	Censored
1.	Progression documented between scheduled visits	4.	Date of assessment of progression ¹	4.	Event
1.	No progression (or death) or initiation of new anti-cancer therapy	5.	Date of last 'adequate' assessment of response ²	5.	Censored
1.	Received subsequent anti-cancer therapy prior to the date of documented events	6.	Date of last 'adequate' assessment of respnose ^{2,3} (prior to initiation of anti-cancer therapy)	6.	Censored
1.	Death before first PD assessment (or Death at baseline or prior to any adequate assessments)	7.	Date of death	7.	Event
1.	Situation	1.	Date of Event (Progression/ Death) or Censoring	1.	Outcome Event (Progression/ Death) or Censored
----	---	----------	---	----	--
1.	Death or progression after more than one missed visit	8. 9.	Date of last 'adequate' assessment of response ² (prior to missed assessments) Refer to Section 15.7.2	8.	Censored

 The earliest of (i) Date of radiological assessment showing new lesion (if progression is based on new lesion); or (ii) Date of radiological assessment showing unequivocal progression in non-target lesions, or (iii) Date of last radiological assessment of measured lesions (if progression is based on increase in sum of measured lesions)

- 2. An adequate assessment is defined as an assessment where the Investigator determined response is CR, PR, SD, or Non-CR/Non-PD.
- 3. If PD and new anti-cancer therapy occur on the same day, assume the progression was documented first e.g., outcome is 'progression' and the date is the date of the assessment of progression). If anti-cancer therapy has started prior to any adequate assessments, censoring date should be the start date of treatment.

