To evaluate the preliminary effects of fed versus fasted administration on the pharmacokinetics of GSK3326595	GSK3326595 PK parameters in plasma following single-dose administration of GSK3326595 in a fed or fasted state
 To evaluate the relative bioavailability of GSK3326595 tablets as compared to capsules 	GSK3326595 PK parameters in plasma following single-dose administration of GSK3326595 in tablet or capsule formulation
Exploratory	

Part 2 (Dose Expansion)				
Objectives	Endpoints			
Primary				
To determine clinical activity of GSK3326595 in disease-specific expansion cohorts	 Solid tumor (non-glioblastoma multiforme, GBM) cohorts: Overall response rate (ORR, defined as % of subjects achieving CR and PR) based on RECIST 1.1 criteria GBM cohort: Six-month progression free survival (PFS) rate, defined as the percentage of subjects free from radiographic progression per Response Assessment in Neuro-Oncology (RANO) criteria, or death due to any cause, for six months after starting GSK3326595. Non-Hodgkin's lymphoma cohort(s): ORR (% of subjects achieving CR and PR) based on Lugano criteria 			
Secondary				
 To further describe the clinical activity of GSK3326595 	 PFS, defined as time from first dose until radiographic progression per standard criteria, or death due to any cause, whichever is earlier. 			
	 GBM cohort: Overall Response Rate (CR + PR) based on RANO Working Group criteria 			
	 ACC tablet cohort: Duration of response (DOR), defined as time from first evidence of response (CR or PR per RECIST 1.1) to earlier date of disease progression or death due to any cause, as determined by Investigator assessment 			
	 ACC tablet cohort: Overall survival (OS), defined as time from first dose until death from any cause in ACC subjects who are systemic-treatment naïve 			
 To evaluate the safety and tolerability of GSK3326595 in subjects treated at the RP2D 	 AEs, SAEs, dose reductions or delays, withdrawals due to toxicities and changes in safety assessments (e.g., clinical laboratory parameters, vital signs, physical examinations, and organ-specific parameters). 			
Exploratory				

Part 2 (Dose Expansion)		
Objectives	Endpoints	
CCI		

Part 3 (Combination with Pembrolizumab)			
Objectives	Endpoints		
Primary			

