- Partial response (PR): Greater than or equal to a 50% reduction, compared to baseline, in the sum of products of the perpendicular diameters for all measurable lesions for at least 4 weeks, no progression of non-measurable disease, no new lesions, and stable or improved nonenhancing (T2/FLAIR) lesions. In addition, subject must be on a corticosteroid dose not greater than the dose at the time of baseline scan and be stable or improving clinically. In the absence of a confirming scan 4 weeks later, this response will be considered only stable disease.
- Progressive Disease (PD): Greater than or equal to a 25% increase in sum of the products of perpendicular diameters of enhancing lesions (compared with baseline if no decrease) on stable or increasing doses of corticosteroids, OR a significant increase in T2/FLAIR nonenhancing lesions on stable or increasing doses of corticosteroids compared with baseline scan or best response after initiation of therapy, not due to comorbid events, OR the appearance of any new lesions, OR clear progression of non-measurable lesions, OR definite clinical deterioration not attributable to other causes apart from tumor, or to decrease in corticosteroid dose. Failure to return for evaluation as a result of death or deteriorating condition should also be considered as progression.

TMF-14123404

CONFIDENTIAL

• Stable disease (SD): If subject does not qualify for CR, PR, or PD and has stable nonenhancing (T2/FLAIR) lesions on same or lower doses of corticosteroids compared with baseline scan and clinically stable status. In the event that the corticosteroid dose was increased for new symptoms and signs without confirmation of disease progression on neuroimaging and subsequent follow-up imaging shows that this increase in corticosteroid dose was required because of disease progression, the last scan considered to show stable disease will be the scan obtained when the corticosteroid dose was equivalent to the baseline dose.

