Increase in corticosteroid dose alone, in the absence of clinical deterioration related to tumor, will not be used as a determinant of progression. Subjects with stable imaging studies whose corticosteroid dose was increased for reasons other than clinical deterioration related to tumor do not qualify for stable disease or progression. They should be observed closely. If their corticosteroid dose can be reduced back to baseline, they will be considered as having stable disease; if further clinical deterioration related to tumor becomes apparent, they will be considered to have progression. The date of progression should be the first time point at which corticosteroid increase was necessary.

The definition of clinical deterioration is left to the discretion of the treating physician, but it is recommended that a decline in the Karnofsky Performance Status (KPS) from 100 or 90 to 70 or less, a decline in KPS of at least 20 from 80 or less, or a decline in KPS from any baseline to 50 or less, for at least 7 days, be considered neurologic deterioration unless attributable to comorbid events or changes in corticosteroid dose. Similarly, a decline in the Eastern Cooperative Oncology Group and world health organization (WHO) performance scores from 0 or 1 to 2 or 2 to 3 would be considered neurologic deterioration.

Subjects with non-measurable enhancing disease whose lesions have significantly increased in size and become measurable (minimal bidirectional diameter of ≥ 10 mm and visible on at least two axial slices that are preferably, at most, 5 mm apart with 0-mm skip) will also be considered to have experienced progression. The transition from a non-measurable lesion to a measurable lesion resulting in progression can theoretically occur with relatively small increases in tumor size (e.g., a 9 X 9mm lesion [non-measurable] increasing to a 10 X 11mm lesion [measurable]). Ideally, the change should be significant (>5 mm increase in maximal diameter or $\geq 25\%$ increase in sum of the products of perpendicular diameters of enhancing lesions).

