In general, if there is doubt about whether the lesion has progressed, continued treatment and close follow-up evaluation will help clarify whether there is true progression. If there is uncertainty regarding whether there is progression, the subject may continue on treatment and remain under close observation (e.g., evaluated at 4-week intervals). If subsequent evaluations suggest that the subject is in fact experiencing progression, then the date of progression should be the time point at which this issue was first raised.

14.4.3. Evaluation, Staging and Response Assessments for Non-Hodgkin's Lymphoma: The Lugano Classification (according to Cheson, 2014)

Evaluation, staging, and response criteria are summarized in 3 tables below.

Criteria for Involvement of Site

Tissue Site	Clinical	FDG Avidity	Test	Positive Finding
Lymph nodes	Palpable	FDG-avid histologies	PET-CT	Increased FDG uptake
		Non-avid disease	СТ	Unexplained node enlargement
Spleen	Palpable	FDG-avid histologies	PET-CT	Diffuse uptake, solitary mass, miliary lesions, nodules
		Non-avid disease	СТ	> 13 cm in vertical length, mass, nodules
Liver	Palpable	FDG-avid histologies	PET-CT	Diffuse uptake, mass
		Non-avid disease	СТ	Nodules
CNS	Signs, symptoms		СТ	Mass lesion(s)
			MRI	Leptomeningeal infiltration, mass lesions
			CSF assessment	Cytology, flow cytometry
Other (e.g., skin, lung, GI tract, bone, bone marrow)	Site dependent		PET-CT ^a , biopsy	Lymphoma involvement

Abbreviations: CSF, cerebrospinal fluid; CT, computed tomography; FDG, fluorodeoxyglucose; MRI, magnetic resonance imaging; PET, positron emission tomography.

a: PET-CT is adequate for determination of bone marrow involvement and can be considered highly suggestive for involvement of other extralymphatic sites. Biopsy confirmation of those sites can be considered if necessary.

Stage	Involvement	Extranodal (E) Status
Limited		
Ι	One node or a group of adjacent nodes	Single extranodal lesions without nodal involvement
Π	Two or more nodal groups on the same side of the diaphragm	Stage I or II by nodal extent with limited contiguous extranodal involvement
II bulky ^a	II as above with "bulky" disease	Not applicable
Advanced		
III	Nodes on both sides of the diaphragm; nodes above the diaphragm with spleen involvement	Not applicable
IV	Additional noncontiguous extralymphatic involvement	Not applicable

Staging System for Primary Nodal Lymphomas

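### SAP Table 10 applies RECIST-style dating and censoring to the GBM primary 6-month PFS rate, in conflict with the RANO rules in protocol 14.4.2, so the Kaplan-Meier rate could be overstated

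*SAP*

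**What the plan says.** **Protocol**

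- The GBM primary endpoint (Sections 1 and 3) is the six-month "percentage of subjects free from radiographic progression per Response Assessment in Neuro-Oncology (RANO) criteria, or death due to any cause".
- Section 14.4.2 lists, among the alternative criteria for progression, "definite clinical deterioration not attributable to other causes apart from tumor, or to decrease in corticosteroid dose". It adds: "Failure to return for evaluation as a result of death or deteriorating condition should also be considered as progression".
- The same section has two back-dating rules. The first covers subjects with stable imaging whose steroid dose was raised for a reason other than tumor-related deterioration and who then deteriorate because of tumor: "The date of progression should be the first time point at which corticosteroid increase was necessary". Its limit is explicit: "Increase in corticosteroid dose alone, in the absence of clinical deterioration related to tumor, will not be used as a determinant of progression". The second covers doubtful progression that is later borne out: "then the date of progression should be the time point at which this issue was first raised".

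**SAP**

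- Section 7 and Table 8: response for GBM is the investigator's RANO call, recorded on the eCRF.
- Section 7.1.3: PFS ends at documented progression or death. "The PFS rate at 6 months for Part 2 GBM cohort will be estimated by the Kaplan-Meier method".
- Table 10 censors a living subject without any assessment after baseline at treatment start. It censors a progression or death that follows more than one missed visit at the last adequate assessment. Section 15.7.3.4 sets the gap for cohorts other than NHL at 119 days (16 weeks plus 7 days).
- Footnote 1 to Table 10 offers three progression dates: a scan showing a new lesion, a scan showing non-target progression, or "Date of last radiological assessment of measured lesions (if progression is based on increase in sum of measured lesions". Footnote 2 includes Non-CR/Non-PD, a category in the protocol's RECIST 1.1 section and not among its RANO categories.
- Section 2.1 declares no deviation from the analysis planned in Amendment 8.

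**The concern.** The response criteria for this cohort are RANO, but the rules that turn responses into PFS times are written for RECIST. RANO treats non-return because of deterioration as a failure, whereas Table 10 can remove the same subject from the risk set. That censoring is informative: those removed are the subjects doing worst, and Kaplan-Meier then assigns them the experience of those who kept attending.

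Scans may not repair this. Table 14 (footnote 17) requires an end-of-treatment scan only if the last one was more than 8 weeks earlier and progression is undocumented. Continued radiological follow-up after stopping treatment is specified only for the ACC tablet cohort (Protocol 5.4.1 and 8.7.1). A GBM subject who stops because of deterioration soon after a scan may never have a radiological progression date.

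At stake is a single-arm primary estimate read against a fixed 17% historical rate, in at most 28 subjects.

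**Working it through.** **1. The design figures reproduce and are not in dispute.** An exact binomial recursion over the Table 18 futility bounds (n = 10 to 27), followed by success at 8 or more of 28, gives type I error 0.0859 at 17% and power 0.806 at 35%. The protocol states 0.086 and 80%. Every stopping probability in Table 18 agrees to four decimals.

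**2. The rules side by side.**

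| Situation | Protocol 14.4.2 | SAP Table 10 and 15.7.3.4 |
|---|---|---|
| Alive, too ill to return for any scan after baseline | Progression | Censored at treatment start |
| Non-return because of deterioration; progression or death found after more than one missed visit | Progression | Censored at last adequate assessment |
| Clinical deterioration recorded as progression by the investigator | Progression | Documented progression, but footnote 1 has no date for it |
| Stable imaging, steroid raised for another reason, then tumor-related deterioration | Progression, back-dated to the increase | No rule |
| Doubtful progression later borne out | Progression, dated to when first raised | No rule |

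The second row in numbers: month 6 is 6 × 30.4375 = 182.6 days, or 26.1 weeks. A subject last scanned at week 8 (day 56), too ill for the week-16 and week-24 scans, who dies after about day 56 + 119 = 175, is censored at week 8. Under 14.4.2 that subject had already progressed before month 6.

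**3. Size if censored on day 1.** With x subjects progression-free at month 6 and complete follow-up in the rest, the Kaplan-Meier rate is x/28. Censoring m of the failures on day 1 gives x/(28 − m). For x = 7 (assumed):

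- m = 0: 7/28 = 25.0%
- m = 1: 7/27 = 25.9%
- m = 2: 7/26 = 26.9%
- m = 3: 7/25 = 28.0%
- m = 4: 7/24 = 29.2%

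**4. Size if censoring is spread over visits.** Assume 5 of 28 progression-free (0.179), with failures at weeks 8, 16 and 24 numbering 13, 6 and 4.

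- One failure censored on day 1: 15/27 × 9/15 × 5/9 = 0.185.
- One censored at week 8 instead: 15/28 × 9/14 × 5/9 = 0.191.
- Three censored, one each on day 1, at week 8 and at week 16: 15/27 × 9/14 × 5/8 = 0.223.
- Six censored (3, 2 and 1 at those times): 15/25 × 9/13 × 5/8 = 0.260.

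The number progression-free is 5 of 28 in every case.

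**5. Censoring compared with re-dating.** A simulation assumed exponential PFS, 8-week scans and a share f of progressions that are clinical only. With a true rate of 17%, the 6-month Kaplan-Meier estimates were:

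| f | Clinical PD an event on its date | Event, dated at next scan | Censored at last scan |
|---|---|---|---|
| 10% | 0.191 | 0.193 | 0.219 |
| 20% | 0.186 | 0.192 | 0.250 |
| 30% | 0.182 | 0.190 | 0.285 |

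The first column exceeds 0.17 because a scan-detected progression after week 24 is seen only at week 32. The last column is a what-if: the SAP does not say that all clinical progression is censored. Dating at the next scan moves the estimate by 0.02 at most, even with f raised to 50% or the true rate to 35%.

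**6. The success rule.** Protocol 11.3 and SAP 3.1.1 require at least 8 of 28 subjects (28.6%) who are unprogressed and on treatment at month 6. Censoring a subject who has stopped treatment adds nothing to that count.

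**The case against.** The strongest reply is that the protocol's endpoint says radiographic progression, so a scan-dated rule follows the protocol and the tension lies between its endpoint text and its own appendix. That is fair, and the protocol must be reconciled first. It does not clear the SAP. The endpoint also counts death from any cause, which Table 10 censors after more than one missed visit, and SAP 7.1.3 speaks of documented progression without the radiographic limit.

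A reader might infer that the SAP censors every clinical progression. It does not. No row censors progression recorded by the investigator, documented progression is an event, footnote 1 hangs on an event row, and SAP 15.6.3 assigns progression the earliest disease-assessment date. What remains is that 15.6.3 and footnote 1 are not tied together for a progression without a scan.

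A reader might also infer that RANO dates progression generally to a steroid increase, so that an increase in weeks 22 to 26 followed by progression on the week-32 scan is a failure before month 6. The documents do not establish that. The steroid rule covers one narrow scenario that ends in clinical deterioration. Where later imaging explains the increase, 14.4.2 fixes only the last scan that counts as stable.

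Finally, a Kaplan-Meier figure of 29.2% should not be set against the 8/28 threshold, because the two are different analyses. Only a re-dated subject kept on treatment across month 6 could alter the count. Protocol 5.4.1 permits treatment through equivocal progression, so this is possible but narrow.

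**Conclusion.** The point holds as a conflict between stated rules. Table 10 and SAP 15.7.3.4 censor some subjects whom protocol 14.4.2 counts as progressed, and they supply no PFS date for clinical-deterioration progression or for the two back-dating rules, while SAP 2.1 declares no deviation. Censoring failures can only raise the Kaplan-Meier 6-month rate, so it could be overstated. The documents do not support saying that it is: they do not give the number of subjects affected.

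Under the assumptions shown, one to four subjects censored on day 1 raise 25.0% to between 25.9% and 29.2%, and three censored across the visits raise 17.9% to 22.3%. Re-dating alone has little effect on average. The 8/28 success count is largely protected by its on-treatment condition, and the design's error rates are unaffected.

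**What to change.** 1. Reconcile the endpoint's radiographic wording with protocol 14.4.2, and state whether clinical RANO progression is a primary event.
2. Add GBM-specific rows to Table 10. Investigator-recorded RANO progression is an event on its recorded date. Non-return because of death or deterioration, taken from the discontinuation reason or the death record, is an event and not a censoring.
3. Apply the steroid-increase and first-raised date rules only within the terms of 14.4.2.
4. Report the scan-only version as a sensitivity analysis, and list this change in SAP 2.1.

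The cost is SAP wording and one derivation for at most 28 subjects. The 6-month rate may come out slightly lower. Reasons for non-return may be incompletely recorded. Protocol 7.1 requires drug, dose and dates for concomitant medication but does not list the reason for a dose change, and Amendment 8 stops data collection for subjects off treatment. The report should therefore say how many subjects could not be classified.

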7.2. Secondary Efficacy Analyses

7.2.1. Confirmed Overall Response Rate (ORR) based on RECIST 1.1 for Part 1 Cohorts

Best response will be estimated as described in Section 7.1.1 and will be summarized by dose levels for Part 1.

7.2.2. Confirmed Overall Response Rate (ORR) based on RANO Criteria for Part 2 GBM Cohort

Best response will be estimated as described in Section 7.1.1 and will be summarized by dose levels for Part 1. The RANO criteria will be used to ascertain response (Wen, 2010). In comparison to RECIST 1.1 criteria, RANO criteria does not require a minimum of 49 days to assign as response stable disease (SD).

7.2.3. Confirmed Overall Response Rate (iORR) based on iRECIST for Part 3 Cohort

Overall response rate based on iRECIST (iORR) is defined as the percentage of participants with a best overall response (iBOR) of "immune" complete response iCR or immune partial response iPR (Seymour, 2017). "Immune" best overall response (iBOR) will be summarized by dose levels for Part 3. The derivation of iBOR per iRECIST will be as follows:

- Progressive disease is "confirmed (iCPD) in the new lesion category, if the next imaging assessment, done at 4–8 weeks after iUPD, confirms additional PD, i.e., new lesions or a further increase in new lesion size from iUPD (sum of measures increase in new lesion target ≥5 mm, any increase for new lesion non-target)"(Seymour, 2017).
- iSD, iPR, or iCR can still be assigned if one or more instances of iUPD occurred at a previous visit. However, iCR, iPR, and iSD cannot be assigned if iCPD occurred at a previous visit.

• To be assigned a status of iSD, follow-up disease assessment must have met the iSD criteria at least once after the first dose for a minimum of 49 days.

iBOR takes into account the requirement for confirmation of iCR, iPR, and iPD. If iBOR is iUPD and is confirmed consecutively, iBOR will be termed as iCPD. If iBOR is iUPD but not confirmed, there is no subsequent iSD, iPR, or iCR (e.g., NE or lost follow-up), the iBOR will be termed as iUPD. If iBOR is iUPD but not confirmed and the subject died or discontinued treatment or has initiated new anticancer therapy after this PD assessment, the iBOR will be termed as iCPD.

Examples of scenarios of assignments of confirmed/unconfirmed iBOR (assuming the adjacent timepoints are 28 days apart at least) are provided in the following table:

Casea	Time point	Time point	Time point	Time point	Time point	Confirmed	Unconfirmed
0400	Response 1	Response 2	Response 3	Response 4	Response 5	iBoR	iBoR
1	iCR	iCR	iCR,iPR,	iUPD	iCPD	iCR	iCR
			iUPD, or NE				
2	iUPD	iPR, iSD, or	iCR	iCR	iCR, iPR, iSD, iUPD,	iCR	iCR
		NE			iCPD, or NE		
3	iUPD	iPR	iPR, iCR	iPR, iSD,	iPR, iSD, iUPD, NE,	iPR	iCR
				iUPD, NE, or	or iCPD		
				iCPD			
4	iUPD	iSD or NE	iPR	iSD	iSD,iUPD, iCPD, or	iSD	iPR
					NE		
5	iUPD	iSD	iSD, iUPD, or	iSD, iUPD,	iSD, iUPD, iCPD, or	iSD	iSD
			NE	iCPD, or NE	NE		
6	iUPD	iCPD	Any	Any	Any	iCPD	iCPD
7	iUPD	iUPD	iCPD	Any	Any	iCPD	iCPD
		(no iCPD)					
8	iUPD	NE	NE	NE	NE	iUPD	iUPD
9	iUPD⁵					iCPD	iCPD

Table 11Examples of iBOR Assignments

BOR = best overall response; CPD = confirmed progressive disease; CR = complete response; iRECIST = immune Response Evaluation Criteria in Solid Tumors; NE = not evaluable; PR = partial response; RECIST = Response Evaluation Criteria in Solid Tumors; SD = stable disease; UPD = unconfirmed progressive disease. NOTE: "i" indicates immune responses assigned using the iRECIST evaluation criteria

^a Assume any two adjacent assessments are at least 28 days apart

^b Last assessment before the subject died/discontinued from treatment

7.2.4. Progression Free Survival (PFS) for Part 1, Part 2 (non-GBM), Part 3

Progression-free survival (PFS) will be estimated by cohorts for Part 2 as described in Section 7.1.3. RECIST 1.1 criteria will be used for non-NHL cohorts, and Lugano criteria for NHL cohorts. Estimates of 1st quartile survival, median survival, and 3rd quartile survival will be presented with 95% confidence intervals based on the Brookmeyer-Crowley method (Brookmeyer, 1982).D

7.2.5. Lesion Analysis – Parts 1, 2, and 3

Change/percent change from baseline based on the sum of target lesion diameters will be calculated by timepoint for all cohorts except NHL and GBM. Change/percent change from baseline based on the sum of target *lesion areas* will be calculated by timepoint for the *GBM cohort*. The following figures will be produced:

- Percent change from baseline in target lesions over time (spider plot) all cohorts except NHL.
- Best change from baseline in target lesions (waterfall plot) all cohorts except NHL.
- Treatment duration along with the overall response, the best change from baseline in target lesions, etc. (swimmer plot).

7.2.6. DOR and TTR for Part 2 ACC TN Cohort based on RECIST 1.1 Criteria

Duration of response (DOR) based on RECIST 1.1 for the Part 2 ACC TN cohort will be listed and summarized for subjects with a confirmed CR or PR and is defined as the time (in months) from first documented evidence of CR or PR until the first documented sign of disease progression or death, for the subset of subjects with a confirmed CR or PR. Censoring rules will follow those of the PFS analysis.

If there are a sufficient number of responders who subsequently progress or die due to PD, median DoR, first and third quartiles and 95% CI, will be estimated using the Brookmeyer-Crowley method (Brookmeyer, 1982).

Time to response (TTR) is defined as the time from date of first dose to date of first documented evidence of PR or CR among participants who achieve a response (i.e. PR or CR). A listing of TTR will be provided for the ACC TN cohort only.

